3.1.2 Primary and secondary outcomes

[figure not shown]
Primary and secondary outcomes are presented in in Table 3. Outcomes will be assessed during initial care (the date of enrollment to 14 days) and follow-up (30 days after initial care) unless otherwise specified.

Table 3. Primary and secondary outcomes

Measure	Description
Hospital admission rate at initial episode of care	The rate of initial hospitalization for the treatment of ABSSSI
Total admitted hospital days during initial care and follow up	Includes days during the initial hospitalization (for those initially hospitalized) and all other hospitalizations
Infection-related total admitted hospital days during initial care and follow up	Includes days during the initial hospitalization (for those initially hospitalized) and all other infection-related hospitalizations
ED length of stay at initial episode of care (time from triage to release from ED)	Time spent in ED in hours from triage to release (either admitted to the hospital, admitted to observation, or released to home)
Infection-related major surgical interventions that required operating room time during initial care and follow up	Number of major unexpected surgeries
	Number of major expected surgeries
	Number of all major surgical interventions unexpected or expected
Infection-related hospitalizations during initial care and follow up	Number of infection-related hospitalizations

Measure	Description
Infection-related hospitalizations during initial care and follow-up that resulted in admission to Intensive Care Unit (ICU)	Number of infection-related hospitalizations resulting in admission to the ICU.
All cause hospitalizations in the 30 days post discharge from the hospital or release from the ED	Number of all hospitalizations for subjects discharged from the ED and re-hospitalizations for subjects who had an initial hospital admission
Infection-related ED visits during initial care and follow up	Number of unexpected visits to ED
	Number of expected visits to ED
	All visits (unexpected and expected) to ED
Infection-related outpatient healthcare visits (e.g., physicians' office visits, ED visits, infusion center visits, home health visits) during initial care and follow up	Unexpected visits, by site (e.g., physicians' office visits, ED visits, infusion center visits, home health visits)
	Expected visits, by site (e.g., physicians' office visits, ED visits, infusion center visits, home health visits)

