4.4 Secondary Outcomes

[figure not shown]
[figure not shown]
Secondary outcomes will be assessed during initial care (the date of enrollment to day 14) and/or follow-up (30 days after initial care), and include:

[figure not shown]
[figure not shown]
Measure	Definition	Period of Assessment
Total admitted hospital days	Total LOS during the 44 days of the study (including initial hospitalization)	Initial care and follow-up
Infection-related total admitted hospital days	Total LOS of all infection related hospitalizations during the 44 days of the study (including initial hospitalization)	Initial care and follow-up
ED LOS	Time spent in ED in hours from triage to release (either admitted to the hospital, admitted to observation, or released to home)	Initial episode of care
Infection-related major surgical interventions that required operating room time	Number of all, unexpected and expected infection-related major surgical interventions that required operating room time	Initial care and follow-up
Infection-related hospitalizations	Number of infection-related hospitalizations	Initial care and follow-up
Infection-related hospitalizations that resulted in admission to intensive care unit (ICU)	Number of infection-related hospitalizations resulting in admission to the ICU.	Initial care and follow-up
All cause hospitalizations in the 30 days following discharge from the initial hospitalization or release from the initial ED visit (if not hospitalized)	Number of all hospitalizations for patients discharged from the ED and re-hospitalizations for patients who had an initial hospital admission	Overall, including Initial care and follow-up
Infection-related ED visits	Number of all, unexpected and expected infection-related ED visits	Initial care and follow-up

Measure	Definition	Period of Assessment
Infection-related outpatient healthcare visits (e.g., physicians' office visits, ED visits, infusion center visits, home health visits)	Number of all, unexpected and expected infection-related outpatient healthcare visits, generated for all patients and repeated by site.	Initial care and follow-up
Use of PICC line or central line to administer antibiotic therapy	Number of PICC line or central line placement for antibiotic therapy	Initial care and follow-up

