6.1.3 Rounding

Means and medians will be rounded to one decimal more than that which the variable was recorded. Standard deviations will be rounded to two decimals more than that which the variable was recorded.

Percentages will be rounded to the nearest integer. Percentages for responses to a variable will only include patients with non-missing data, i.e. the denominator will be the number of patients with non-missing data.

P-values will be reported to three decimal places. Probabilities that are <0.001 will be presented as " <0.001 ."

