6.1.5 Handling of missing and/or incomplete data

Patients will be missing specific data points for a variety of reasons. With the exception of validated instruments, missing values for a given time point will not be imputed and analyses will be conducted using an observed case approach. For validated instruments, missing items will be handled according to instructions from the relevant scoring manuals.

Where both date and time are collected, partial times (i.e. times with missing minutes or times with missing hours and minutes) will be estimated by a worst-case imputation approach (e.g., impute such that duration is the longest possible value). Analyses will be conducted using an observed case approach for partial or missing dates.

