Healthcare resource utilization within the 3 months prior to study enrollment will be reported in tables by the pre-period and post-period for the FAS population. Number of patients and percentages of occurrences (e.g., none, any, 1, 2, ≥ 3) and primary reasons for the following will be reported: hospitalizations, admissions to the ICU, surgical interventions, and ED or outpatient visits. Descriptive statistics will also be presented for these variables. Additionally, number of patients and percentages of coded diagnoses terms will be reported for hospitalizations and admissions to the ICU and number of percentages for specified surgical procedures. The number and percentages of patients with minor and major surgical procedures will be displayed. The table will also reflect the number and percentages of patients with dialysis use, prior medications used for chronic diseases, prior use of antibiotics, and wound care for the presenting infection. Listings for hospitalizations will capture the type of visit, primary reason for visit, primary diagnosis (coded and verbatim), admission date and time, discharge date and time, ICU admissions for hospitalizations and discharge disposition. Prior antibiotic medications will be reported in a listing and will include start date and end date, medication named (coded and verbatim), reasons for prescription, dose with units and frequencies, route, and reason for discontinuation.

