6.2.6 Outcomes

6.2.6.1 Primary Outcomes

Primary Outcome: Hospital Admission Rate at Initial Episode of Care

Hospital admission at initial episode of care will include infection-related stays upon discharge from the index ED visit (derived and described in Appendix B). Tables will reflect patient counts and percentages for hospital admission (yes, no) at the initial episode of care by the pre-period and post-period for the FAS population. Summary rows will be repeated by site.

The primary analysis will consist of hypothesis testing using a one-sided, two-sample Pearson chi-square test for proportion difference with a normal approximation. An appropriate alternative method will be selected if a major violation to an assumption is present.

Because the baseline characteristics of the pre-period may differ from those of the post-period, a secondary analysis using a multivariate logistic regression analyses will be implemented. This model will assume mutual independence between the sites.

Clinically relevant baseline characteristics of interest for the adjusted analysis include the following variables: age, gender (Male, Female), race (White/Caucasian, Black or African American, Other), employment status (Full-Time, Part-Time, None), insurance plan type (Private commercial plan, Government funded, Uninsured, Other), Charlson Comorbidity Index, lesion surface area (<75cm², =>75 cm² – 150 cm², >150 cm²), infection type (Wound infection, Cellulitis/erysipelas, Abscess), prior health resource use (Yes, No, Unknown), prior antibiotic treatment failure (Yes, No, Unknown), presence of SIRS criteria (<2 or >=2), presence of recurrent infection in prior 6 months (Yes, No, Unknown), any health resource use in prior 3 months (Yes, No, Unknown), as well as is patient was immunocompromised (Yes, No, Unknown). Patients will be defined as immunocompromised if they have evidence of any of the following at baseline: Connective tissue disease, diabetes mellitus, leukemia, or malignant lymphoma. Categorical variables will be collapsed where possible. The primary predictor variable will be a pre/post-period indicator, and potentially other selected characteristics will be forced into the model based on clinical rationale and distributions observed in the

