Appendix B: Derived Variables

Analysis Section (Visit)	Variable (Units)	Definition
General (Baseline)	Enrollment date	Informed consent date
General (Baseline)	Baseline date	Initial ED admission date
General (Initial Care)	Initial care indicator	If enrollment date \leq date \leq enrollment date + 13 days then = Yes Else = No
General (Follow-up)	Follow-up indicator	If enrollment date + 14 \leq date \leq enrollment date + 43 days then = Yes Else = No
Demographics (Baseline)	Age (years)	Round down to nearest integer((Initial ED admission date - date of birth + 1)/365.25), when both dates are available.
Demographics (Baseline)	BMI	weight (kg)/ [height(m)] ² Where necessary, height and weight will be converted to proper units.
Infection Characteristics (Baseline)	CCI	Will be scored as described in Appendix C. Includes variables for raw score and 10 year survival probability.
Infection Characteristics (Baseline)	Fever	If temperature > 38 ° C then =Yes Else =No
Infection Characteristics (Baseline)	Morbid Obesity	If baseline BMI \geq 40 then =Yes Else =No
Infection Characteristics (Baseline)	SIRS Criteria Met	SIRS criteria include abnormalities in temperature, heart rate, respiration, and white blood cell count. Specifically included are: 
 Fever of more than > 38.0°C or hypothermia with temperature < 36.0°C

[figure not shown]
[figure not shown]
Analysis Section (Visit)	Variable (Units)	Definition
		
 • Tachycardia with heart rate > 90 beats/minute or • Tachypnea with respiratory rate of > 20 breaths/minute or PaCO₂ of less than 32mmHg • Abnormal white blood cell count: leukocytosis >12,000/microliter, leucopenia <4,000/microliter, or >10% immature cells (bands).^{3,4} 
If 2 or more criteria present = Yes Else = No

Antibiotic Medications (Initial Care and Follow-up)	Days Received Antibiotic Medication	
Σ (Medication end date – Medication start date +1), when both dates are available. If dates overlap (e.g., end date and next start date are identical) then subtract 1 from summation for each occurrence.

Primary Outcome	Hospital Admission At Initial Episode of Care	
If discharge destination from the initial episode of care = Hospital and the reported hospitalization where discharge date = hospital date is infection-related then = Yes, Else = No

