Secondary Outcomes (All visits)	Hospitalization LOS (days)	
For all-cause: Σ (Hospitalization end date – Hospitalization start date +1), when both dates are available. If ongoing at end of study or discontinuation date, use study completion date or discontinuation date as end date. For outcomes, LOS will be computed two ways: only in-patient hospitalizations visits and inpatient hospitalizations visits with prolonged observation

[figure not shown]
Analysis Section (Visit)	Variable (Units)	Definition
		
status (e.g., time in observation status exceeds 1 day).
 
For infection-related: Subset all-cause hospitalization time for patients with infection-related hospitalization stays

Secondary Outcomes (End of Study Visit)	Completers Flag	
If "Did the patient complete the study?" = 1 on the end of study visit CRF page and date of study completion does not equal missing, then =Yes, Else = No
 
This flag will be used to repeat certain primary and secondary outcomes that could be influenced by early discontinuation (e.g., LOS)

Secondary and Other Outcomes (Initial episode of care)	ED LOS (hours) Observation Status LOS (hours)	
Impute with estimated time where applicable for partial times. if admission date = discharge date then LOS (hours) = discharge time - admission time
 
else LOS (hours) = sum all hours over stay, with a full day counting as 24 hours

Secondary Outcomes (Follow-up)	WPAI	Scores and coded variables will be derived as described in Appendix D.
Secondary Outcomes (Initial Care and Follow-up)	SF-12	SF-12 sub-scores and total scores will be compiled using the Health Outcomes Scoring Software 5.0 by QualityMetric Inc. Further detail can be found in Appendix E.
Adverse Events (Baseline, Initial Care and Follow-up)	Highest severity AE	Severity of most severe AE for the patient with order of severity: Severe>Moderate>Mild Patients who only have AEs reported with missing severity,

Analysis Section (Visit)	Variable (Units)	Definition
		highest severity AE will be reported as missing

[Redacted]

[Redacted]

[Redacted]

[Redacted]

[Redacted]

[Redacted]

[Redacted]

[Redacted]

[Redacted]

[Redacted]

[Redacted]

[Redacted]

[Redacted]

[Redacted]

[Redacted]

[Redacted]

[Redacted]

[Redacted]

[Redacted]

[Redacted]

[Redacted]

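### The primary-outcome rule codes a direct infection-related admission as not admitted when discharge date and hospital date fall on different calendar days

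*SAP*

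**What the plan says.** The Protocol, section 3.1.2 (Table 3), describes the primary outcome as "The rate of initial hospitalization for the treatment of ABSSSI". It sets no condition on dates.

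SAP 6.2.6.1 adds the restriction to infection and the starting point: "Hospital admission at initial episode of care will include infection-related stays upon discharge from the index ED visit". It then refers to Appendix B for the derivation.

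The Appendix B row gives Yes when "discharge destination from the initial episode of care = Hospital and the reported hospitalization where discharge date = hospital date is infection-related". All remaining cases are No. The row has no tolerance in days, no link by time or by episode, and no category for missing.

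Two general rules sit elsewhere in the SAP. Section 6.1.5 says: "Analyses will be conducted using an observed case approach for partial or missing dates". Section 6.1.3 says that for percentages "the denominator will be the number of patients with non-missing data".

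**The concern.** The two definitions in words ask whether the patient went from the index visit into hospital for the infection. The derivation asks that, and also whether two recorded dates are the same calendar day. The extra condition is an artefact of how stays are matched and has no clinical meaning. It fails for a real admission whenever the recorded departure and the recorded start of the stay lie on either side of midnight. The mismatch can run in either direction, since the hospital date may fall after or before the departure date.

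Such a patient is not set aside for checking. The catch-all turns the patient into a non-admission who stays in the denominator. The primary objective is to estimate the between-period difference in this proportion, so the recorded rates should match the stated definition. Equal loss in both periods shrinks the difference and does not raise the false-positive rate. If loss differed between periods, the comparison would be biased: more loss in the post-period would overstate the reduction, and more loss in the pre-period would understate it.

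**Working it through.** **Reading the rule.** Take a patient with destination Hospital, an infection-related stay, departure at 23:40 on one day and a hospital date of the next day.

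- Protocol Table 3: initial hospitalisation for the infection, so counted.
- SAP 6.2.6.1: infection-related stay on leaving the index ED visit, so counted.
- SAP Appendix B: the dates are not equal, so No.

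**Inputs from the documents.** Admission rates 38% and 23%, one-sided 0.05, power at least 80% (SAP 6.1.2); 161 per period (SAP 3.0); originally assumed attrition 10% (SAP 5.0), which leaves 0.9 × 161 = 144.9, about 145.

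**Input that is assumed.** The share of true admissions lost to the date match. If every admission had its two times recorded g hours apart, and departures were spread evenly over the day, the share crossing midnight would be g/24. For 1 hour this is 4.2% and for 2 hours 8.3%. I use 4% and 8%. This is a high scenario, because it gives every admission such a gap.

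**Formula.** Normal approximation with pooled variance under the null, n per period and p̄ = (p₁ + p₂)/2:

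power = Φ{ [ (p₁ − p₂)√n − 1.645 √(2p̄(1 − p̄)) ] / √(p₁(1 − p₁) + p₂(1 − p₂)) }

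**The plan's own figure first.** For 0.38 vs 0.23 and n = 161: (0.15 × 12.689 − 1.645 × 0.6511) / 0.6424 = 1.296, so power is 90.2%. At n = 145 it is 87.4%. The stated floor of 80% holds.

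**Equal loss m in both periods.** The recorded rates are 0.38(1 − m) and 0.23(1 − m).

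| m | Recorded rates | Difference | Power, n = 161 | Power, n = 145 |
|---|---|---|---|---|
| 0 | 38.0% vs 23.0% | 15.0 points | 90.2% | 87.4% |
| 4% | 36.5% vs 22.1% | 14.4 points | 88.7% | 85.6% |
| 8% | 35.0% vs 21.2% | 13.8 points | 87.0% | 83.7% |

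Solving for power of 80% gives m of about 21% at 161 and 15% at 145.

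**Unequal loss, illustration only.** True rate 38% in both periods, n = 161, nominal one-sided error 5%.

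| Loss pre | Loss post | Chance of a superiority finding |
|---|---|---|
| 4% | 5% | 5.8% |
| 4% | 6% | 6.6% |
| 5% | 4% | 4.3% |
| 6% | 4% | 3.7% |

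**The case against.** The strongest reply is that no passage shows that departure and hospital dates ever differ, that all loss rates above are assumed, and that a record with destination Hospital but no date-matched stay contradicts itself and would be noticed. Protocol 3.2 provides logic checks and queries, SAP 6.1.9 double programming and statistical review, and SAP 7.0 a listing of hospital, ED and observation visits. This stands as far as size goes. It does not remove the point: two correctly recorded dates on either side of midnight give a query nothing to correct, and the rule would still return No.

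Four stronger readings are tempting, and the documents do not support them.

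- *Missing data are wrongly coded as not admitted.* Read literally, the catch-all does this. But SAP 6.1.5 and 6.1.3 already give a general observed-case rule, and the Fever, Morbid Obesity and SIRS rows use the same bare form, so it may be shorthand. For a patient released home there is no hospital date or flag to record, and No is correct.
- *The SAP itself expects such gaps.* The ED length-of-stay row has a branch for stays that span days ("sum all hours over stay, with a full day counting as 24 hours"). That branch compares dates within one ED or observation stay. It does not compare leaving the ED with entering the hospital.
- *Patients moved from observation to an inpatient bed are lost.* SAP 6.2.6.1 starts from the index ED visit, and Appendix B from the initial episode of care. If observation belongs to that episode, the destination is Hospital and the patient can be counted. The ED length-of-stay entry in SAP 4.4 ("Time spent in ED in hours from triage to release (either admitted to the hospital, admitted to observation, or released to home") lists observation as a separate release, but it defines a secondary outcome. This is wording to reconcile and no demonstrated error.
- *The primary test is biased.* That needs loss that differs by period, which nothing in the documents shows.

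**Conclusion.** The date-match point holds. As written, Appendix B is narrower than the outcome it is meant to derive, and it codes some true admissions as non-admissions. The finding rests on the text alone and needs no assumption about frequency.

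Its size does rest on assumption. With equal loss of 4–8% the difference shrinks by 0.6–1.2 points and power at 161 per period by about 1.5–3.2 percentage points, and the stated 80% is kept even after 10% attrition. SAP 5.0 says that observed attrition exceeded 10% without giving the value, so the margin may be smaller than the 145 column shows. The direction and size of any bias from unequal loss cannot be determined from the documents. I rate the point minor, but worth correcting because it concerns the only primary outcome.

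**What to change.** Replace the equality of dates in the Appendix B row, before the period comparison is run:

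1. If the recorded destination is Hospital, link the index episode to the next infection-related inpatient stay dated within one calendar day of discharge, with no discharge home in between, and code Yes.
2. If the recorded destination is anything other than Hospital, code No.
3. If the destination is missing, or is Hospital but the linked stay's date or infection-related flag is still missing after query, treat the outcome as missing under SAP 6.1.5.
4. Use one term for the starting point in SAP 6.2.6.1 and Appendix B, and state how an observation stay that becomes inpatient is handled.

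Step 3 is not free of bias, because a missing stay date or flag can arise only in a patient sent to hospital. If 5% of admitted patients were dropped, the rates would be 0.361/0.981 = 36.8% and 0.2185/0.9885 = 22.1%, a difference of 14.7 points. Coding them No would give 36.1% − 21.85% = 14.25 points.

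The cost is a few lines in Appendix B and a short programming check of stays whose dates differ. The one-day tolerance uses dates that the present rule already needs. Linking by time would be tighter, but the SAP text that lists "admission date and time, discharge date and time" concerns use in the prior three months, so the availability of times for index hospital stays should be confirmed first.

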3.2.1 Data collection schedule

Table 5 describes expected follow-up. Follow-up visits will be scheduled for 24 hours after enrollment (post-period only), between 48-72 hours after enrollment (post-period only), 14 days after enrollment (both periods), and 44 days after enrollment (both periods). The follow-up visits during the post-period include a telephone call at 24 hours and a limited physical visit at 48-72 hours. However, for subjects unable to be seen back at the site, a telephone interview will suffice at 48-72 hours. Research data will be collected through follow-up visits at 14 days (telephone call can occur between 14 and 21 days from enrollment) and at 44 days (telephone call can occur between 44 and 51 days from enrollment), through a telephone interview of the subject in both the pre- and post-periods. Additionally, electronic medical chart data will be reviewed at the 14 day and 44 day time points from enrollment. Any additional visits to the visit schedule below will be at the discretion of the subject and treating physician.

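### The SAP's hospital-days formula counts a shared transfer date twice and does not cap stays at the 44-day window; it should count distinct dates and truncate at enrollment + 43

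*SAP*

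**What the plan says.** SAP Section 4.4 defines total admitted hospital days as "Total LOS during the 44 days of the study (including initial hospitalization". The infection-related version has the same 44-day scope.

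SAP Appendix B derives the variable by summing over stays: end date minus "Hospitalization start date +1), when both dates are available". For a stay still ongoing at study end or at discontinuation, the instruction is to "use study completion date or discontinuation date as end date". The variable is computed twice, once on inpatient stays only and once adding prolonged observation of more than one day.

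Three other entries bear on it:

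- The antibiotic-days row of Appendix B uses the same end-minus-start-plus-one sum. Where an end date equals the next start date, it adds: "then subtract 1 from summation for each occurrence".
- Appendix B sets the initial-care window at enrollment to enrollment + 13 and the follow-up window at enrollment + 14 to enrollment + 43. Enrollment is the "Informed consent date"; the initial ED admission date is held separately as the baseline date.
- Protocol Section 3.2.1 says of the final contact: "telephone call can occur between 44 and 51 days from enrollment".

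SAP Section 6.2.5.2 reports hospital days descriptively, by initial care, follow-up and overall, without formal testing.

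**The concern.** The antibiotic-days row shows that the authors saw that adding one per record double-counts a date shared by two records. The hospital-days row has the same structure and no such correction. A transfer between facilities on one date is therefore counted twice. So is an observation stay converted to inpatient on one date, in the second version of the variable, if the two are recorded as separate stays.

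The closing rule for ongoing stays refers to a date that need not lie inside the outcome window, so the days counted for such a stay could depend on when a telephone call was made.

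The SAP also does not say whether a day is a calendar date touched or a night. The choice matters for an absolute difference between periods with different admission rates.

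At stake is the estimate itself. SAP Section 2.2 sets the secondary objective as estimating between-period differences. Total admitted hospital days is listed first there, and Protocol Section 5.3 records that it was the primary outcome before the interim analysis.

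**Working it through.** **The plan's own figures.** The documents give no worked result for this variable. Their one related calculation is for the primary outcome (SAP Section 6.1.2: 322 subjects, 161 per period, 38% versus 23%, one-sided 0.05, at least 80% power). It reproduces: the pooled normal approximation needs 116 per period, and power at 161 is 90.2%. That calculation does not use the hospital-days formula.

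**1. Shared dates.** Take one patient with stays on days 0–2 and 2–4.

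- Hospital-days formula: (2 − 0 + 1) + (4 − 2 + 1) = 6.
- Distinct dates (0, 1, 2, 3, 4): 5.
- Nights: (2 − 0) + (4 − 2) = 4.
- Antibiotic-row rule applied to the same dates: 6 − 1 = 5.

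Six is wrong under either definition of a day. For the effect on the difference, assume that the same share of admitted patients in each period has one such transfer. At 10% the double count adds (0.38 − 0.23) × 0.10 = 0.015 day per patient; at 20% it adds 0.15 × 0.20 = 0.03. The documents do not give the share.

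**2. No cap.** Let a stay start on day s inside the window and still be ongoing when the study ends. If completion is dated to a call on day 51, the formula gives 51 − s + 1; the part inside the window is 43 − s + 1. The excess is 51 − 43 = 8 days, whatever s is. If completion is dated to day 44, the excess is 44 − 43 = 1 day.

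**3. The plus one.** Assume one stay per admitted patient, L nights per stay in both periods, and the planning rates of 38% and 23%. The difference per enrolled patient is 0.15 × (L + 1) by the formula and 0.15 × L in nights.

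| Nights per stay (assumed) | Difference, formula | Difference, nights |
|---|---|---|
| 1 | 0.30 | 0.15 |
| 2 | 0.45 | 0.30 |
| 3 | 0.60 | 0.45 |
| 4 | 0.75 | 0.60 |
| 5 | 0.90 | 0.75 |

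The gap is 0.15 day throughout. The relative reduction is 1 − 0.23/0.38 = 39.5% either way. That invariance needs equal stay length. With 2 nights before and 3 after, the reduction is 1 − 0.69/0.76 = 9.2% in nights and 1 − 0.92/1.14 = 19.3% by the formula. Against a count of calendar dates, the plus one causes no error for a single stay.

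**The case against.** Much of the case on the other side stands.

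- End minus start plus one is an ordinary inclusive count. Nothing in either document defines a day as a night, so a reader who infers from the table that the formula inflates the saving (by a third at 3 nights, 0.60 against 0.45) has supplied the definition. What remains is that the convention is undeclared.
- Day 51 is the end of a call window. The available text does not define the completion date as the call date, and Protocol Section 2.3.3 ends follow-up 44 days after enrollment. The 8 days is therefore a conditional ceiling. Few stays should be affected, since SAP Section 5.0 reports a mean stay well below the assumed 4.0 days, and the rule is the same in both periods.
- Observation time enters only the second version of the variable, and only beyond one day. The transfer effect is small at the shares tried.

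A reader might also infer that an index stay begun before consent falls in neither window and is lost, mainly in the pre-period. That needs a rule placing stays by start date, which Appendix B does not state, and it would contradict Section 4.4, which includes the initial hospitalization. Consent is also expected in the ED, with enrollment anticipated on the day treatment starts. If 5–20% of pre-period stays only were dropped (assumed, 3 nights per stay), the formula difference would fall from 0.60 to between 0.52 and 0.30. That would oppose the effect of the plus one.

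Nor can the effect on costs be established. SAP Section 6.2.12 prices a hospital day but refers to Section 4.6 for detail, which is not in the available text.

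**Conclusion.** The point holds in limited form. The missing shared-date correction is a plain inconsistency between two rows of one appendix, and it produces a count that is wrong under any convention. The missing cap is a conflict between the derivation and the 44-day outcome. It is worth up to 8 days for a stay still ongoing at study end if completion is dated to a day-51 call. The plus one is a convention to declare; compared with nights it shifts the absolute difference by 0.15 day per patient, given the planning rates and one stay per admitted patient.

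The documents do not support the stronger conclusion that the formula biases the comparison in favour of the new pathway. The possible effects run in opposite directions and their frequencies are unknown. Hospital days are secondary and untested, so the primary outcome and the sample size are untouched. The descriptive estimate of the difference is what is exposed.

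**What to change.** Amend the hospital-days row of Appendix B as follows:

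1. Count the union of distinct calendar dates across contiguous or overlapping stays, in both versions of the variable.
2. Truncate every stay at enrollment date + 43, whatever the completion date.
3. Always include the index stay, identified by its link to the initial ED visit and not by comparing its start date with the consent date.
4. State that the result is an inclusive calendar-day count, and add a sensitivity summary in nights (end minus start, minimum 1 per admission).

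If dates are allotted to windows one by one, a stay that crosses from initial care into follow-up divides without a further rule.

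The cost is programming and one extra summary row. The dates are already collected, and no change to data collection, sample size or the primary analysis is needed. The direction in which the reported difference would move cannot be stated in advance.
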